This trial aims to deliver, across a range of UK hospitals, a package of interventions for Acute Kidney Injury (AKI) aimed to improve recognition and quality of care for AKI, and to assess how this translates into better outcomes in AKI patients and if this intervention can reduce the incidence of h-AKI (detailed protocol available on request).

For practical reasons this service can only be applied at the level of the population covered by the hospital and not on a subset of random patients within a hospital. Also the intervention is assumed to have a positive effect on AKI management/outcomes. For these reasons the study has been set up as a stepped-wedge cluster randomised trial (SWCRT), with the intervention applied at a cluster level and applied to all participating units by the end of the study. Such an approach overcomes any ethical problem of withholding a treatment considered likely to be effective, as the entire population recruited will receive the treatment by the end of the study. This approach also allows for differentiation between the effect of the intervention and potential independent unknown time-related factors.

There are no reporting guidelines specific to SWCRTs, so this Statistical Analysis Plan (SAP) is written to be consistent with the extension to cluster randomised trials of the CONSORT 2010 document [Campbell et al., 2012] and further suggestions recently published for SWCRT [Hemming et al, 2015]. This statistical analysis plan will guide the Trial Statistician during the statistical analysis of all quantitative outcomes in order to answer the objectives of the study.

STUDY DESIGN

A Stepped Wedge Cluster Randomised Trial approach will be taken. This means that the intervention will be delivered in sequential steps to one or more units of randomisation per time-period and

delivered to all the units of randomisation by the end of the study. This study has recruited 5 hospitals and is planned to take two years, between December 2014 and November 2016, with 2 initial control periods for all 5 hospitals, followed by 5 steps of randomisation (one hospital per step), and including a transition period (the first 'treatment period', when the treatment is expected not to have reached full efficacy on outcomes), for a total of 8 time-periods, each of 3 months in length (24 months in total – see Table-1, page.6).

THE INTERVENTION

The intervention (protocol, sections 3 and 5, available on request for details), has 3 parts:

- An AKI electronic detection system within pathology laboratory software
- An educational program to raise awareness and knowledge of AKI in care workers at hospital
- An AKI care bundle

The AKI electronic detection system has already been mandated at a national level (England only), with the plan to start nationwide from April 2015. The 5 hospital recruited for this SWCRT have been exempted from the initiative for the time being, so they would be able to wait to implement the intervention at their assigned time of randomisation, while having the electronic detection system in place since the end of 2014, but silent (as to measure the incidence of AKI during the baseline periods, with no active intervention).

OUTCOMES MEASURES

The outcomes of this study will be measured for all adult patients hospitalised overnight in the 5 participating hospitals, and identified as having an episode of AKI while in hospital by the pathology laboratory detection system (with results suppressed, non-visible to end-users, during control periods). The outcomes will be measured for the entire length of the study-period (1st Dec 2014 to 30th Nov 2016) for all of the AKI events, so multiple entries per patient are possible.

Primary outcome

- Thirty-day mortality after an episode of AKI. These are patient level data, binary outcome (0=patient alive 30 days after the AKI episode; 1=patient dead 30days after the AKI episode, logistic analysis).

Secondary outcomes

- 1. Incidence of h-AKI (aggregate data, counts, number of h-AKI cases, defined as AKI developed after >24hrs in hospital, with the denominator at risk being the total overnight hospitalisation episodes, Poisson analysis, standardised).

- 2. Incidence of AKI progression (defined as AKI that increases by at least one stage of AKI from AKI-stage at time of first detection) during hospitalisation. These are patient level data, binary outcome for each episode of AKI (0=did not progress during hospitalisation; 1=progressed during hospitalisation, logistic analysis).
As we will not be able to determine for all patients diagnosed with level-3 AKI if they progress to need of acute dialysis during hospitalisation, we will perform this analysis to the cohort of AKI level-1 and level-2 episodes only.
- 3. Incidence of individual AKI stages (stage 1, stage 2 and stage 3). These are aggregate data, counts, to analyse as secondary outcome n-1.
- 4. Length of hospital stay of patients with AKI (patient level data, counts in days, potentially to analyse using Poisson model, depending on the distribution of this outcome)
- 5. Number of critical care bed days used by patients with AKI (patient level data, counts of days in ICU for each patients, possibly to analyse using Poisson or negative binomial model zero inflated, depending on distribution, as many counts of zeros are expected.
- 6. Achievement of complete renal recovery by hospital discharge in AKI patients (with renal recovery defined as serum creatinine returning to a value less than 27 μ mol/l above baseline creatinine value). These are patient level data, binary outcome on all AKI patients (0=did not recover during hospitalisation; 1=recovered during hospitalisation, logistic analysis).

RANDOMISATION UNITS AND TIME-PERIODS

In this trial, the primary outcome will be measured for each episode of AKI detected in patients hospitalised overnight, while the intervention will be implemented at hospital level. Hence this is a cluster randomised trial, where the units of randomisation are the participating hospitals.

In this trial the intervention will be implemented in a total of 5 hospitals, with only one hospital being randomised each time at each step (with a total of 5 randomisation steps), with time periods of 3 months length.

This intervention is complex and would take some time to deliver it. While the electronic detection system has been set up in advance (with results kept suppressed at baseline) and can be activated immediately at start of intervention, teaching to staff will require some time as well as change in practice to be established. For these reasons we expect to observe no quantifiable effects on the outcomes of AKI patients at first after intervention, and hence we have planned to have a transition period. While data on primary and secondary outcomes will be collected for all periods of the study, data from the transition period for each hospital will be excluded from the analyses. As this trial has sufficient power, we have planned for the transition period to be of the same length as the unexposed/exposed time-periods (3 months).

In summary (see Table-1), we are planning to have, for each hospital, two or more control periods (unexposed to the intervention, coded as '0'), one transition period (the first period of intervention,

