Randomisation was performed using SAS-9.3 (RANUNI function), to generate 5 random numbers.

These were then allocated to the five hospitals (listed in alphabetical order, based on hospital name), and finally the hospitals were sorted based on their random numbers, from smallest to highest, giving the sequence of randomisation.

DATA SOURCE, COLLECTION AND VALIDATION

Data from hospitals

All data used for the analyses described in this document will be collected as part of routine clinical care, from electronic hospital records. Patient level data will be extracted from the hospitals' PAS for all patients flagged by the AKI electronic detection system. The data extracted will be sent to the UKRR. If data are sent in separate files, each file will need to contain unique patient identifiers to allow subsequent linkage and removal of duplicates by the UKRR.

Data set (see <https://www.thinkkidneys.nhs.uk/wp-content/uploads/2014/12/AKI-Warning-Algorithm-Best-Practice-Guidance-final-publication-0112141.pdf> for details) will include:

- Patient identifiers and demographics:
 - NHS number or Local Patient Identifier
 - Date of birth
 - Gender (M/F/U)
 - Ethnicity (name/code)
- Date of admission and date of discharge
- Primary specialty (text field)
- Charlson co-morbidity score (numeric score) and constituent chronic disease binary scoring (1=present, 0=absent)
- In hospital mortality (numerical field, 1=died in hospital 0=survived to discharge)
- 30 day mortality (numerical field, 1=died within 30days of first AKI warning stage result 0=survived to >30days)
- Date of death (date field)
- Length of hospital stay (numerical, in days)
- ICU admission (1=admitted to ICU during hospital stay, 0=no ICU admission) and ICU admission length of stay (numerical field in days)
- AKI data (see <https://www.thinkkidneys.nhs.uk/wp-content/uploads/2015/01/Transmitting-AKI-Warning-Stage-Data-to-the-UKRR-final.pdf> for detailed specification): initial AKI warning stage (numerical field limited to 1, 2 or 3), highest AKI warning stage (numerical field limited to 1, 2 or 3), time between admission and first AKI Warning stage result (numerical field, in hours), final inpatient creatinine result to assess recovery (numerical field, micromol/l).

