The primary outcome (30 day mortality) is the only outcome that will be observed in a fixed time interval starting at date of admission rather than during the hospitalisation spell. While some hospitalisation spells will last one month or more, most will be shorter. As we have previously pointed out, multiple episodes (hospitalisations with AKI) in the same patient can occur. This is not a problem when the outcome is related exclusively to the hospitalisation spell (duration, ICU, recovery, progression). However in the analysis of 30 day mortality the presence of multiple episodes could create a problem, if the multiple episodes should occur within a month. For example a patient could be hospitalised with AKI for a week, return at home and re-hospitalised a second time after a week, and die in hospital after few days, in which case the patient will be present twice in the cohort, both times with an outcome of death within 30 days. For this reason, only in this analysis, we will exclude repeated AKI-episodes that occur within a month from the previous hospitalisation, whichever the outcome. A case like the one just described will appear only once in the dataset, while a patient that is hospitalised with AKI for a week, then is back at home for 4 weeks, and then re-hospitalised with AKI again will appear twice.

Analysis of 30-day mortality will be done using a mixed-effects logistic regression, as a patient level analysis, and accounting for correlations between episodes in the same hospital by including hospital in the model as a random effect. If a non-insignificant proportion of episodes of AKI should be multiple episodes in same patients, we will also account for the correlation between episodes in the same patient by fitting a second random effect for patient in the analysis. The primary outcome response

will be binary (patient died by 30days after AKI=1, patient still alive after 30days since AKI=0). Mortality is expected to decrease after the intervention.

The odds ratio estimate of the mortality risk for the treatment effect (intervention versus control) with 95% confidence interval will be presented (Model-1). Analysis will be adjusted by time-period (step) (Model-2) and individual patients' characteristics (Model-3) such as age at hospitalisation, gender, possibly ethnicity, and Charlson comorbidity score.

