The as-treated analysis will include all cases of AKI as ‘control’ or ‘treated’ based on the treatment that patients had received at time of AKI episode, rather than the treatment they were assigned based on the allocation process. In this case 1st day of the month when e-alert was activated in each hospital will be considered the start of that hospital’s transition period.

The report will include adherence to the timing of randomisation to intervention.

NOTE: If a logistic model should not run/iterate then we will use an equivalent mixed-effects linear regression analysis, approximating by using 0 and 1 as a continuous variable for the dichotomous variable of 30 days mortality (Hussey and Hughes, 2007).

Analysis of secondary outcomes

- The aggregate-data secondary outcomes 1 and 3 (incidence of h-AKI and incidence of AKI by level of AKI - expressed as number of patients developing AKI per hospitalised population), will be analysed using a Poisson regression, standardised by age and gender and, if possible, by ethnicity.

This will be a cluster-level Poisson analysis, with one measure per time-period per hospital, if unadjusted (or one measure per time-period per hospital per age-gender subgroup, if standardised).

MODEL
$$\text{Log}(Y_{ij}) = \log(\text{exposure}_{ij}) + \theta * T_{ij} + \gamma_j + \alpha_i$$

Where Y_{ij} = count of AKI episodes in hospital I at time J

Exposure-ij=denominator, number of hospitalisations in hospital I at time J

θ = effect of the treatment variable (T=1 exposed, T=0 control) in centre I at time J

γ = effect of Time (vector if effect not linear)

(+ ωQ_{ij} in the model if we want to investigate interaction between Time and Treatment)

- For secondary outcome n-2 (progression of AKI, binary outcome), we will use the same analysis as for the primary outcome (mixed-effect logistic regression), limited to the cohort of episodes classified as level-1 and level-2 AKI at time of first detection.

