- The analysis of length of hospital stay (see outcome 4, page-5) in patients with AKI will be done with the model most appropriate to the distribution of this outcome. As these data are count data (days in hospital, integers ≥ 1), Poisson analysis with episode-level data, adjusted for clustering at centre, is expected to be appropriate. However if the distribution should be approximate to normal or over-dispersion should be observed, mixed-effect linear regression or negative binomial models will be considered. The same model building sequence will be used as in the logistic analysis of the primary outcome.
- Number of critical care bed days (outcome 5, see page 5), will be analysed based on the distribution of the outcome. This is a count outcome, expected to be zero inflated, therefore a negative binomial analysis will be considered if over-dispersion is observed, or logistic regression if very little dispersion is observed for this outcome (0=No days in ICU, 1=one or more days in ICU).
- For secondary outcome n-6 (recovery of AKI, binary outcome, see page-5), we will use the same analysis as for the primary outcome (mixed-effect logistic regression). In this analysis, if patient should die during hospitalisation before recovery of function, the episode will be counted as a non-recovery, while if patient recovers renal function during hospital stay but then dies, the episode will still be considered as a recovery.

TIMELINE FOR ANALYSIS

	Dec 2014 - Nov 2015				Dec 2015 - Nov 2016				Dec 2016 - Nov 2017			
	D-F	M_M	J-A	S-N	D-F	M_M	J-A	S-N	D-F	M_M	J-A	S-N
Develop statistical analysis plan												
Randomise units to steps												
Baseline period-1												
Baseline period-2												
1st Transition												
2nd Transition												
3rd Transition												
4th Transition												
5th Transition												
Last period, all on treatment												
Provide 1 st report on data												
Statistical analysis and write up												

REFERENCES

Balasubramanian, G., et al., *Early nephrologist involvement in hospital-acquired acute kidney injury: a pilot study*. Am J Kidney Dis, 2011. 57(2): p. 228-34.

Chawla, L.S., et al., *Acute kidney injury and chronic kidney disease as interconnected syndromes*. N Engl J Med, 2014. 371(1): p. 58-66.

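### AKI progression (secondary outcome 2) scores in-hospital death without a stage rise as no progression, and the plan does not show these deaths separately by exposure

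*SAP*

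**What the plan says.** The SAP (Outcomes measures, Secondary outcomes, item 2) defines progression as "defined as AKI that increases by at least one stage of AKI from AKI-stage at time of first detection" and codes each episode "0=did not progress during hospitalisation; 1=progressed during hospitalisation, logistic analysis". Under Analysis of secondary outcomes it adds: "For secondary outcome n-2 (progression of AKI, binary outcome), we will use the same analysis as for the primary outcome", "limited to the cohort of episodes classified as level-1 and level-2 AKI at time of first detection". That cohort is not restricted to survivors.

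The relevant fields are listed under Data source, collection and validation: the initial warning stage and the "highest AKI warning stage (numerical field limited to 1, 2 or 3"). The same list includes "In hospital mortality (numerical field, 1=died in hospital 0=survived to discharge") and the date of death.

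For renal recovery (secondary outcome 6), Analysis of secondary outcomes does give a rule for deaths: "if patient should die during hospitalisation before recovery of function, the episode will be counted as a non-recovery". It also says that a patient who recovers renal function and then dies remains a recovery. Outcome 2 has no corresponding sentence.

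On the expected direction, Analysis of primary outcome says: "Mortality is expected to decrease after the intervention". The Sample size calculation works with a fall in 30-day mortality from 16% to 12.8%.

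**The concern.** Death in hospital ends the opportunity to progress, so it is a competing event for outcome 2. The coding puts two very different courses into the same 0: the patient who improved and went home, and the patient who died before the stage could rise.

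This would matter little if such deaths were equally frequent under control and exposure, but the trial is built on the expectation that they are not. If mortality falls, patients who would have died with a score of 0 survive longer, and some may go on to progress and score 1. Measured progression could then look worse under the intervention without any harm to the kidney. If early mortality rose instead, progression could look better for the wrong reason. The odds ratio for outcome 2 alone cannot separate an effect on progression from an effect on survival.

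**Working it through.** **How a death is scored.** Take a stage 1 episode whose highest stage is still 1 when the patient dies in hospital. Highest equals initial, so there is no rise and the score is 0. The episode was stage 1 at first detection, so it is in the cohort. No text excludes it, counts it as a failure or treats it as a competing event. This follows from the definition and the data fields; the SAP has no sentence about deaths for this outcome.

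**Plan figures.** The SAP states no rate or power for progression. The figure used here is the planned mortality reduction: (16 − 12.8) / 16 = 20%, as the SAP says. The cluster-period size also reproduces: 434,000 × 0.025 / (5 × 4) = 542.5, against about 540. The share of stage 1 and 2 episodes is not given, so the shift below cannot be turned into a count of episodes.

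**Inputs for the shift.**
- r = 0.20, the relative reduction in deaths, from the SAP, assumed to apply to in-hospital deaths without progression.
- d, the share of stage 1 and 2 episodes that die in hospital before progressing under control: not in the SAP; assumed 5% to 16%.
- q, the chance that a patient whose death is averted later progresses: not in the SAP; assumed 10% to 50%.
- p, progression under control: not in the SAP; assumed 10% to 20%.
- The intervention's own effect on progression is set to zero.

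**Formula.** Rise in measured progression = d × r × q. With p1 = p + d × r × q, the odds ratio is [p1 / (1 − p1)] / [p / (1 − p)].

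| d | q | p | Rise (points) | Odds ratio |
|---|---|---|---|---|
| 5% | 10% | 20% | 0.05 × 0.20 × 0.10 = 0.1 | 1.006 |
| 10% | 25% | 20% | 0.10 × 0.20 × 0.25 = 0.5 | 1.031 |
| 10% | 25% | 10% | 0.5 | 1.056 |
| 16% | 25% | 10% | 0.16 × 0.20 × 0.25 = 0.8 | 1.090 |
| 16% | 50% | 10% | 0.16 × 0.20 × 0.50 = 1.6 | 1.181 |

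At q = 0 there is no shift for any d. For scale, the planned mortality effect has odds ratio (0.128 / 0.872) / (0.16 / 0.84) = 0.77.

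**Composite of progression or in-hospital death, same mechanism.** Control rate = p + d; exposed rate = p + 0.8d + 0.2dq. With p = 15%:
- d = 10%, q = 20%: 25.0% to 23.4%, odds ratio 0.92.
- d = 16%, q = 20%: 31.0% to 28.4%, odds ratio 0.88.
- Over d = 5% to 16% and q = 10% to 50%: odds ratios 0.87 to 0.97.

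For d = 10% to 16%, q = 20% and p = 15%, the present coding gives 1.03 to 1.05. The way deaths are scored can therefore decide on which side of 1 the estimate falls, even with no effect on progression.

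**The case against.** The strongest reply is that nothing is stated wrongly. A patient who died without a stage rise did not progress as the plan defines progression, so the score of 0 is accurate and the issue is which quantity the trial wants to estimate. That stands, and it is why the definition should be kept.

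A reader might infer that outcomes 2 and 6 treat the same death in opposite ways. The text does not support this. Both record whether the named renal event occurred during the stay: death before recovery is scored as not recovered, and death before progression as not progressed. What differs is which value is favourable. Because recovery followed by death stays a recovery, outcome 6 does not treat every death as failure either.

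A reader might also infer that outcome 2 should simply become progression or death. That would have its own problem. With no effect on progression, the composite moves further from 1 at q = 20% (0.88 to 0.92) than the present coding does (1.03 to 1.05), because it brings the primary outcome into a measure of progression. Without an exception, it would also count recovery followed by death as a failure, contrary to the rule for outcome 6.

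The size is open to challenge too. The 16% is 30-day mortality over all stages. It includes stage 3 episodes, deaths after discharge and deaths after progression, so as a value for d it is probably high, although it omits in-hospital deaths after day 30. A q of 50% is far above any of the assumed progression rates.

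Finally, Table-3 already lists 30-day deaths and numbers progressed by hospital and exposure. It does so in separate rows, however, so deaths without progression cannot be recovered from it.

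**Conclusion.** The point holds as a competing-event issue on one secondary outcome. In-hospital death without a stage rise is scored as no progression, and the plan's own hypothesis implies that such deaths will differ by exposure. If progression is otherwise unaffected, averted deaths can only raise measured progression or leave it the same. The illustrated shift is 0.1 to 1.6 percentage points (odds ratio about 1.01 to 1.18). It rests on assumed values of d, q and p and on applying the planned 20% reduction to this group of deaths. The true size cannot be fixed from the SAP and is probably modest.

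The stronger statement, that preventing deaths will raise measured progression, goes too far. If deaths are averted because progression is halted, or if progression truly falls by more than the shift, the measured rate can go down. The primary analysis and the sample size are unaffected.

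**What to change.** Keep the definition and coding of secondary outcome 2. Add to its paragraph under Analysis of secondary outcomes:

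1. A report by exposure of three categories among stage 1 and 2 episodes: progressed; died in hospital without progression; discharged alive without progression.
2. A sensitivity analysis with the same mixed-effects logistic model in which in-hospital death before progression counts as failure. Patients who recover renal function and then die should be handled consistently with the rule for outcome 6, so that they are not counted as failures here and successes there.

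In-hospital death, date of death, and initial and highest stage are already collected, so no new data are needed. The cost is a few sentences, one table and one further model. The composite mixes in deaths not due to AKI and overlaps with the primary outcome, so it should be read beside outcome 2 and not replace it.
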